#### 8.2.5. Supplementary Analyses

The supplementary Estimands for the primary endpoint are the On-IP and the On-Treatment Estimands (see Section 2) and will utilize the ITT Analysis Set (see Section 5.2). The same negative binomial regression model as applied for the main analysis will be implemented for this Estimand (see Section 8.2.1). The analysis will be repeated by including all exacerbations designated "Clinically Relevant" by the adjudication committee per Section 11.3 of the CEC Charter. The same model will be used as for the primary analysis including the combining of PEs as discussed in Section 6.7.1.1.

### 8.2.6. Subgroup Analyses

Consistency of observed treatment effect on the Annualized Rate of PEs will be explored across major subgroups as shown in the list below.

- Age (12-<18, 18-<65 years,  $\ge$ 65 years); (<75 years,  $\ge$ 75 years); (>=18 years),
- Sex (Male, Female),
- All race groups (American Indian or Alaska Native, Asian, Black or African American, Native Hawaiian or Other Pacific Islander, White, Other)
- Ethnicity (Hispanic or Latino, Not Hispanic or Latino),
- Number of PEs in prior 12 months ( $<3, \ge 3$ ),
- Chronic use of Antibiotics at Baseline (Yes, No),
- Maintenance use of macrolides at Baseline (Yes, No),
- Pseudomonas aeruginosa colonization at Baseline (Positive, Negative),
- (Re-calculated) BSI score ( $\leq 4, 5-8, \geq 9$ ),
- Baseline BSI score (< Median, ≥ Median),
- BE-CT score ( $\leq$  Median,  $\geq$  Median),
- Baseline FEV1 % Predicted (<50%, ≥50%) post-bronchodilator,
- Stratification region (North America, Europe, Japan, the Rest of World),
- Geographical region (South America, Eastern Europe, Western Countries, Asian Countries, Oceania)
- Baseline eosinophil count (>=300/mm3, <300/mm3),
- Smoking status (Former smoker, Never smoked,),
- Use of inhaled steroids (Yes, No),
- History of Asthma, identified through MedDRA coded terms (see Appendix K) (Yes, No),
- History of Chronic Obstructive Pulmonary Disease, identified through MedDRA coded terms (see Appendix K) (Yes, No),

CONFIDENTIAL Page 56 of 139

• Hospitalized in prior 24 months for PE (Yes, No).

Subgroup analysis will be based on a similar negative binomial model as used for the primary analysis (see Section 8.2.1). The covariate of age group will not be included in models for subgroup analyses. One model per subgroup parameter will be fitted, omitting the fixed effect if it's identical to the subgroup or confounded with the subgroup. Crosstabulation of subgroup levels versus covariate levels via PROC FREQ will be utilized to identify any confounding. The ITT Analysis Set (see Section 5.2) will be used. A summary for each level of subgroup presenting the same data as for the primary analysis will be produced. A forest plot with annualized rate ratio of PEs and 95% CI will be displayed for each level of all subgroup parameters.

For adolescent subgroup (Age 12-<18), a Bayesian approach that borrows information from the adult subgroup (Age >= 18) will be explored to inform efficacy on the primary endpoint. The prior distribution of the Bayesian approach will be a mixture of a non-informative prior and a distribution of the treatment effects in adults, with the mixing weight ranging from 0 (no borrowing) to 1 (full borrowing) in increments of 0.05 to allow a complete view of the spectrum of outcome The analysis will be performed for each dose separately. The posterior mean and 95% credible intervals will be calculated for each weight value and presented in a figure.

The analysis for the annualized rate of PEs in the adult subgroup (Age >= 18) will also be conducted for the On Treatment Estimand.

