# 10.1. Sample Size and Power Considerations

The study is designed to demonstrate superiority of brensocatib treatment at 10 mg and/or 25 mg over matching placebo as measured by the primary efficacy endpoint of the rate of PEs over the 52-week treatment period. Assuming the annualized PE rate in the placebo arm is 1.2 events with a negative binomial distribution with dispersion of 1, 1620 adult subjects will yield 90% power if the ratio of exacerbation rate is 0.70 (brensocatib over placebo) between any of the brensocatib treatment arms and placebo after 52 weeks of treatment. This estimate is based on study-wise two-sided Type I error of 0.01 or 0.005 for each primary comparison between brensocatib and placebo.

Randomization will be stratified based on a geographic region (North America, Europe, Japan, and the Rest of the World), Screening sputum sample positive or negative for *Pseudomonas aeruginosa*, and the number of prior PEs  $(2, \text{ or } \ge 3)$  in the previous 12 months.

It is well known that among subjects with NCFBE, there is significant heterogeneity across regions in terms of distribution of phenotypes, baseline lung function, symptom scores, presence of comorbidities, and treatment patterns (Jauhiainen et al., 2020; Rabe et al., 2019). The ASPEN study was launched with a global outreach to more than 30 countries so that meaningful conclusions could be drawn on the effect of brensocatib in a representative population. Furthermore, the study was designed to ensure an adequate representation of all types of standards of care and of individual phenotypes worldwide.

In order to have a representative population of NCFBE across all regions, enrollment targets have been established for adult subjects. Up to 13% of subjects will come from Eastern Europe. North America, Western Europe, Asia Pacific, and Latin America will contribute between 20%

and 30% each. No single country (except the US) will contribute more than 15% of the overall randomized population.

In order to have a representative population in the study, similar to what is described in the literature, randomization will be enforced to have approximately 30% of adult subjects with 3 or more prior PEs, to have no more than 20% of subjects older than 75 years of age, to have approximately no more than 20% of subjects with eosinophil count in peripheral blood ≥300/mm³ at Screening, and to have no more than 20% of subjects with COPD as a comorbidity.

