# 10.4.6.5. Subgroup Analyses

Consistency of observed treatment effect on the rate of PEs will be explored across major subgroups as shown in the list below, if deemed appropriate.

- Age (12 to <18 years, 18 to <65 years,  $\ge$ 65 years; <75 years,  $\ge$ 75 years)
- Sex (Male, Female)
- Race (White, Asian, American Indian or Alaska Native, Black or African American, Native Hawaiian or Other Pacific Islander, Other)

- Ethnicity (Hispanic or Latino, Not Hispanic or Latino)
- Number of PEs in prior 12 months  $(1, 2, or \ge 3)$
- Chronic use of antibiotics at Baseline (Yes, No)
- Maintenance use of macrolides at Baseline (Yes, No)
- Pseudomonas aeruginosa colonization status at Baseline (Positive, Negative)
- Baseline BSI score ( $\leq 4$ , 5 to 8,  $\geq 9$ )
- Baseline BSI score (< median, ≥ median)
- Baseline CT scan score (< median, ≥ median)
- Baseline FEV1 % Predicted (<50%,  $\ge50\%$ )
- Geographical region (North America, Europe, Japan, the Rest of World).

Subgroup analysis will be based on a negative binomial model as used for the primary analysis. One model per subgroup will be fitted, omitting the fixed effect if it is identical to the subgroup. The ITT Analysis Set will be used. A summary for each level of subgroup presenting the same data as for the primary analysis will be produced. A forest plot of subgroups with rate of PEs and 95% CI displayed for each level of subgroup.

The main analysis for the primary and secondary endpoints will be repeated for the adolescent subgroup (12- <18 years of age), and separately for the adult subgroup for the On-Study estimand.

Additional subgroup analyses may also be performed if deemed appropriate.

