## 3.2. Sample Size Determination

The study is designed to demonstrate superiority of brensocatib treatment at 10 mg and/or 25 mg over matching placebo as measured by the primary efficacy endpoint of the rate of PEs for adult participants over the 52-week treatment period ( $\geq$ 18 years and  $\leq$ 85 years of age [inclusive] at Screening). Assuming the annualized PE rate in the placebo arm is 1.2 events with a negative binomial distribution with dispersion of 1, a total of 1,620 adult participants randomized in a 1:1:1 ratio to brensocatib 10 mg, brensocatib 25 mg and matching placebo, respectively, will yield 90% overall power to demonstrate that at least 1 dose of brensocatib is superior to placebo under the Truncated Hochberg procedure (overall alpha = 0.01; two-sided test; truncation fraction = 0.9). The ratio of exacerbation rate is assumed to be 0.70 (brensocatib over placebo) between any of the brensocatib treatment arms and placebo after 52 weeks of treatment.

The PK/PD substudy is targeted to enroll approximately 300 participants; the sample size is based on clinical considerations and participant numbers for the PK study.

CONFIDENTIAL Page 19 of 139

<sup>bAdolescents=male or female participants, ≥12 years to <18 years of age at screening

The CT substudy is targeted to enroll approximately 225 adult participants; the sample size is based on clinical considerations and participant numbers for the CT study.

In addition, approximately 40 adolescent participants will be enrolled in a 2:2:1 randomization scheme (16:16:8) to minimize exposure to placebo treatment. The sample size is based on the Sponsor's consultation with several pediatric investigators in this field and from a survey across a number of global sites with pediatric experience conducted by the study contract research organization (CRO). The sponsor believes this proposed sample size will provide an adequate description of the safety profile of brensocatib in this age group and assessment of brensocatib exposure and offer the possibility to observe directional trends in terms of efficacy.

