#### 8.2.1. **Main Analyses**

The Primary Estimand is the On-Study Estimand in which all observed data up to Week 52 will be included in the analysis (see Section 2). The ITT Analysis Set (see Section 5.2) will be used for this Estimand.

The Annualized Rate of PEs will be analyzed using negative binomial regression as implemented in SAS® PROC GENMOD with robust estimate for the covariance matrix. The latter will be achieved by introducing a REPEATED-Statement identifying participant-ID with TYPE=UNSTR^4 for the covariance as unstructured. The model will include treatment group and the randomization stratification factors (sputum sample being classified as positive or negative for *Pseudomonas aeruginosa* at Screening Visit, the number of prior PEs [<3 or ≥3] in the previous 12 months, stratification region [North America, Europe, Japan, and the Rest of the World]), and age group (adult, adolescent) as fixed effects. If the age group covariate creates estimability issues, it may be removed. If the model still does not converge after removing the age group covariate, other handling including using the parametric covariance estimator instead of the robust sandwich covariance estimator may be applied. The time at risk in years (log scale) will be included in the model as an offset variable. The LOG-link function will be used in the model. The OM option will be used to adjust the co-

**CONFIDENTIAL** Page 52 of 139

<sup>4 TYPE=UNSTR option specifies that the covariance matrix of the scores be estimated empirically.

efficients for the LSMEANS to reflect the observed data. An example SAS code can be found in Appendix I.

The annualized Rate of PE for each treatment group, the ratios of PE rates between each brensocatib dose and placebo, and the associated 95% Cis will be estimated from the negative binomial model. In addition, the frequency distribution of participants experiencing 0, 1, 2, 3, and >=4 exacerbations will be provided.

Occurrence of exacerbation events that meet the protocol definition of PE diagnosis based on independent adjudication process will be explored graphically. The below histograms will be produced. Treatment groups will be distinguished by separate bars.

- Count of PEs reported every month in study starting at Day 1 through Week 52. Differentiation of PEs into study month is detailed in Section 6.7.1.7.

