#### 8.3.6. Subgroup Analyses

Subgroup analyses for all secondary endpoints will be reported for the On-Study Estimand based on the groupings defined in Section 8.2.6. However, analyses of QoL-B which is applicable for adults only, will exclude the adolescent subgroup. In addition, the main analysis for secondary endpoints will be repeated for the adolescent subgroup (12-<18 years of age), and separately for the adult subgroup for the On-Study estimand.

Subgroup analysis will be displayed in tabulations and forest plots.

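### The adolescent repeat of the primary analysis (16:16:8) keeps an uncorrected sandwich variance, so its nominal 95% intervals cover about 88%; model-based standard errors alone only partly repair this

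*SAP*

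**What the plan says.** SAP 8.2.1 fits the primary negative binomial model "with robust estimate for the covariance matrix". The SAP's example code (Appendix I) obtains this from a REPEATED statement with one record per participant. The fixed effects are treatment, region, *Pseudomonas* status, prior exacerbations and age group. Parametric covariance is allowed only if the model still fails to converge once age group has been removed.

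SAP 8.2.6 carries this over: "Subgroup analysis will be based on a similar negative binomial model as used for the primary analysis (see Section 8.2.1"). It always drops age group. Any other factor is dropped only if it coincides or is confounded with the subgroup. A rate ratio with a 95% interval is shown for every subgroup level, including age 12 to <18. SAP 3.3 derives *Pseudomonas* status and prior exacerbations for adolescents so that these covariates are available.

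Protocol 10.4.6.5 says "The main analysis for the primary and secondary endpoints will be repeated for the adolescent subgroup". SAP 8.3.6 adds that "the main analysis for secondary endpoints will be repeated for the adolescent subgroup (12-<18 years of age"). For FEV1 the main analysis (SAP 8.3.3.1) is a compound-symmetric repeated measures model with the empirical variance estimator.

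The group is about 40 participants, enrolled in a "2:2:1 randomization scheme (16:16:8"). No small-sample correction, t reference or minimum subgroup size is given for the negative binomial subgroup models.

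**The concern.** The sandwich variance relies on large samples. With 8 participants on placebo and up to five covariate parameters beyond treatment, it tends to be too small, and a normal reference makes the interval narrower still. A model can converge and still give such a standard error, so the non-convergence fallback gives no protection.

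Protocol 1.3.1 aims to support authorization from age 12. The forest plot is where a reader will judge whether adolescents are consistent with adults. An interval labelled 95% that covers about 88% can suggest a benefit or a harm that the data do not support.

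**Working it through.** **1. The plan's own figure.** Protocol 10.1: "Assuming the annualized PE rate in the placebo arm is 1.2 events with a negative binomial distribution with dispersion of 1"; "90% power if the ratio of exacerbation rate is 0.70 (brensocatib over placebo"); "study-wise two-sided Type I error of 0.01 or 0.005 for each primary comparison between brensocatib and placebo". With 540 per arm and an active rate of 1.2 × 0.70 = 0.84:

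Var(log RR) = (1/1.2 + 1)/540 + (1/0.84 + 1)/540 = (1.8333 + 2.1905)/540 = 0.00745, so SE = 0.0863.

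0.3567/0.0863 = 4.13, and 4.13 − 2.807 = 1.32, so power is 90.7%. The stated 90% reproduces.

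**2. The same formula in adolescents.** For 16 against 8, with treatment only:

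SE = √[(1/0.84 + 1)/16 + (1/1.2 + 1)/8] = √(0.1369 + 0.2292) = 0.605.

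Even a correct interval multiplies and divides the estimate by exp(1.96 × 0.605) ≈ 3.3.

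**3. Coverage by simulation.** Small-sample coverage has no simple formula.

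- Counts: negative binomial with variance μ + kμ², arms 16:16:8, one year of follow-up unless stated.
- Assumed, because the documents give no adolescent values: rate 1.2 and k = 1 (adult planning values); region shares 30/40/5/25% (mix 1) or 20/50/0/30% (mix 2); *Pseudomonas* positive 15% to 25%; 3 or more prior exacerbations 30%.
- Fit: log-linear model with maximum likelihood dispersion. Let w = μ/(1 + kμ) and A = Σ w x x′. The model-based covariance is A⁻¹. The sandwich is A⁻¹(Σ s² x x′)A⁻¹ with s = (y − μ)/(1 + kμ). The leverage-corrected (Mancl-DeRouen type) version uses s/(1 − h), where h = w x′A⁻¹x.
- Size: 1,500 to 3,000 trials per adolescent scenario, two dose contrasts each; Monte Carlo SE 0.4 to 0.6 points.

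Coverage of nominal 95% intervals (%):

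| Scenario | Sandwich, z (as planned) | Model-based, z | Model-based, t |
|---|---|---|---|
| All covariates, mix 1, RR 1 | 87.6 | 92.1 | 93.2 |
| All covariates, mix 1, RR 0.70 | 87.5 | 91.4 | 92.7 |
| All covariates, mix 2, RR 1 | 87.9 | 91.9 | 92.8 |
| All covariates, mix 2, RR 0.70 | 88.5 | 91.9 | 93.3 |
| Mix 2, some partial follow-up | 88.2 | 92.2 | 93.7 |
| Dispersion 0.5 | 88.5 | 92.3 | 93.3 |
| Dispersion 1.5 | 86.5 | 91.4 | 92.6 |
| Placebo rate 0.8 | 89.5 | 93.5 | 94.8 |
| *Pseudomonas* and prior PEs only | 89.3 | 93.4 | 94.3 |
| Treatment only, RR 1 (two runs) | 90.1, 90.4 | 93.9, 94.3 | 94.6, 95.2 |
| Treatment only, RR 0.70 | 91.3 | 94.2 | 94.9 |
| Control: 540 per arm | 95.9 | 96.0 | 96.0 |

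The type I error at RR 1 is 100 − 87.6 = 12.4% with all covariates and 100 − 90.1 = 9.9% with treatment only. The control places the shortfall in the small sample.

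**4. Splitting the cause.** In the first row, coverage falls 95 − 87.6 = 7.4 points short. Changing only the covariance recovers 92.1 − 87.6 = 4.5 points. The other 2.9 come from sparse data, covariates and z limits.

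**5. Repairs.** The leverage-corrected sandwich with all covariates (mix 2) covers 95.1% to 95.4% with z and 95.6% to 96.2% with t. Treatment only, model-based with t, covers 94.6% to 95.2%.

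**6. FEV1.** One check of the empirical-variance model at 16:16:8, with complete data and an assumed within-participant correlation of 0.7, gave about 91% (mean SE 0.40 against a true SD of 0.46).

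**The case against.** The best defence is that little depends on this interval. Subgroup consistency is explored, adolescent efficacy is meant to show direction only, and the subgroup lies outside the 12-hypothesis procedure of SAP 6.3. SAP 8.2.6 also plans a Bayesian analysis that borrows from adults, and an interval spanning roughly threefold either way settles nothing. All of this limits the consequence. It does not make the label on the interval correct, and the Bayesian analysis does not alter the forest plot.

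A second defence is that SAP 8.2.6 asks for a similar model and one model per subgroup parameter. Read as a single age-interaction model on all participants, coverage in a check at RR 1 was 91.3%. That softens the figure but leaves it below 95%.

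Third, the inputs are adult values, and adolescents need only one prior exacerbation (Protocol 4.1.1). A lower rate is plausible; at 0.8 coverage was 89.5%.

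Four stronger readings are tempting, and none is supported:

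- *The sandwich is the whole cause.* A reader might infer this from comparing a sandwich model with covariates against a model-based one without. That changes two things at once. In one run with all covariates the true SD was 0.69, the median model-based SE 0.57 and the median sandwich SE 0.52, so much of the gap remains after the switch.
- *The Cox analysis is equally affected.* One check put the Cox sandwich with covariates at about 93% and model-based Cox at about 94%, both close to nominal.
- *Small race groups, or any arm below some size such as 20, fail in the same way.* No calculation supports this or a threshold.
- *The primary result is compromised.* The 540-per-arm control covers 95.9%.

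**Conclusion.** The point holds for the adolescent negative binomial analysis. As planned, nominal 95% intervals cover about 88% (86.5% to 89.5% over the dispersion and rate values examined). Coverage is about 90% to 91% if covariates are dropped or one interaction model is used. The type I error is about 10% to 12% at nominal 5%. These figures rest on adult planning values and an assumed covariate mix, but every reading of the covariate rule that was examined falls short of 95%.

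The cause is the sandwich together with sparse data, covariates and z limits. The evidence for FEV1 is thinner: one check, one assumed correlation. The effect is confined to exploratory adolescent intervals and p-values, and the trial's primary type I error is unaffected.

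**What to change.** Before unblinding, add to SAP 8.2.6, for the adolescent negative binomial analysis, one of:

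- a leverage-corrected (Mancl-DeRouen type) sandwich with the stratification covariates kept; or
- a treatment-only model with model-based covariance and t-based limits.

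State which is chosen, and say whether the adolescent estimate comes from a separate model or an interaction model. Removing the sandwich while keeping all covariates and z limits is not enough.

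For the adolescent FEV1 repeat (SAP 8.3.6), replace the empirical variance with model-based REML and Kenward-Roger degrees of freedom. The SAP's code for the FEV1 slope model already uses that method.

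The cost is a few sentences in the SAP, modest changes to the subgroup code, and somewhat wider adolescent intervals. The primary analysis and the multiplicity procedure do not change.

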## 8.3. Secondary Endpoints

#### **8.3.1.** Time to First Pulmonary Exacerbation

#### 8.3.1.1. Main Analyses

The Main Estimand of the time to first PE is the On-Study Estimand in which all observed data will be included in the analysis (see Section 2). The ITT Analysis Set (see Section 5.2) will be used for this Estimand. The derivation of the endpoint is detailed in Section 6.7.1.6.

Cumulative first PE incidence rates over the 52-Week treatment period will be calculated using the Kaplan-Meier method. The summary will include the number of participants with at least 1 PE and the number of participants without any events (censored). A covariate-adjusted Cox proportional hazards regression model including fixed effects for treatment group, sputum sample being classified as positive or negative for *Pseudomonas aeruginosa* at Screening Visit, the number of prior PEs [<3 or ≥3] in the previous 12 months, stratification region (North America, Europe, Japan, and the Rest of the World), and age group (adult, adolescent) will be fitted using the PHREG procedure with the robust sandwich estimate for the covariance matrix in SAS (option COVSANDWICH(AGGREGATE) in the procedure-statement). If the age group covariate creates estimability issues, it may be removed. If the model still does not converge after removing the age group covariate, other handling including using the parametric covariance estimator instead of the robust sandwich covariance estimator may be applied. The CLASS statement will identify covariates while the model will be identified in the MODEL statement. Results will be summarized in a table including number and percentage of participants with PEs, estimated hazard ratio and 95%

CONFIDENTIAL Page 57 of 139

confidence limits. The 2-sided Wald p-value from the Cox model will be compared to the appropriate alpha level per the multiple test procedure. Technical details for the implementation in SAS can be found in Appendix I.

Kaplan-Meier estimates of the median including 95% confidence interval will be presented.

The effect over time will be illustrated with a plot of the complement (1 - Kaplan-Meier) estimates).

